13.8 Safety Analysis

Rates of hospitalizations and rates of mortality will be compared between the intervention arms as an assessment of safety. Loss of confidentiality and what was done to remedy the loss will also be tracked and reported. In addition, rates of incarceration and detention that are reported through the course of follow up will also be tracked.

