3.0 STUDY FLOW CHART

4.0 INTRODUCTION

4.1 Background

Global experiences over the past 10 years have confirmed the life-saving benefits of ART for treating HIV-positive patients in developing countries.(1-4) However, in many settings, including China, patients are lost at each step along the continuum of HIV care.(5) In Guangxi, where the study will take place, only 50.4% of those who screen HIV-positive at hospital settings receive confirmatory testing, and only 76.0% of those confirmed to be HIV-positive receive their HIV test results. Furthermore, 31.4% of individuals who are notified of their HIV-positive status fail to receive CD4 testing. Since CD4 levels are used to determine ART eligibility (current requirement in China is CD4 \leq 350 cells/mm³ or AIDS diagnosis), it is estimated that nearly 80% of newly-identified, ART-eligible patients in Guangxi are not engaged in ART.(6) These missed opportunities for patient engagement in HIV care ultimately translate into high mortality rates.

[figure not shown]
Other significant barriers to testing and treatment initiation are fear of HIV/AIDS-related stigma(7-9) and patients' inability to meet out-of-pocket costs despite the free ART program.(10) Particular challenges for DUs, who experience late testing and disproportionately low rates of treatment initiation, include fear of registration and detention, and provider perceptions of DUs as being non-compliant patients.(11) Other barriers reported by providers include reluctance to treat HIV-positive patients,(12) insufficient training, limited resource capacity,(13) and uncertainty about recommended guidelines.(14)

In 2011, Guangxi reported the highest number of AIDS-related deaths among all provinces in China, 22% of the national total.(15) The high rate of patient loss to follow-up along the continuum of HIV care is even more pronounced among DUs. As a result, mortality among DUs is also higher. Recent studies of HIV-positive, injecting DUs who are engaged in ART indicate that mortality rates among this population range from 10.4 to 15.9 per 100 person-years.(4, 16)

[figure not shown]

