11.0 STUDY ASSESSMENTS

Data collected for the study will be documented and stored in two online data systems, CRIMS (after confirmed HIV positive) and a web-based database system for study-specific data.

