11.2.2 Follow-up Assessments

Utilizing the hospital-based patient care information systems and CRIMS database, providers will use study-specific CRFs to report participant locator efforts, follow-up visit dates, test results, dates of all test result notifications and all post-test counseling sessions, ART eligibility, and hospitalizations.

Participants who are confirmed HIV-positive (through WB or VL testing) will then have records created in CRIMS, and those data will be available for analysis. The CRIMS forms and assessments are SOC. Basic information collected for CRIMS includes full name, national ID number, date of birth, gender, ethnic group, educational level, marital status, occupation, and date of HIV testing/screening. The CRIMS forms also include detailed information in the following areas:

Medical History

Participants will provide the following information as per routine medical care at the local hospital: history of HIV testing and results, current syphilis, tuberculosis, and hepatitis status, history of former plasma donation, history of blood/blood product transfusion, history of occupational exposure, history of surgeries, suspicious symptoms of tuberculosis, and AIDS-related clinical symptoms.

Sexual Risk Behaviors

Questions will include total number of sex partners in prior 3 months; total number of vaginal sex partners and anal sex partners; total number of unprotected vaginal and anal sex partners; status of HIV infection of the spouses.

Drug Use and Injection Risk Behaviors

Questions will include frequency and amount of use, including heroin, and methamphetamine; frequency and types of drugs injected, and sharing of drugs, needles, and other paraphernalia. We will ask about overdoses and any drug-related hospitalizations.

Confirmatory Testing, CD4 Testing, ART, and Deaths

CRIMS information includes the participant's dates and results of WB, ART, and VL tests. If the participant has initiated ART, his/her date of ART initiation, the ART regimen, and follow-up visits will be recorded in CRIMS. If the patient has died, the date of death will be recorded on CRIMS forms and study CRFs.

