Control arm. A blood sample will be collected from the participant at the study hospital and sent to the local city CDC for WB confirmatory testing. Blood sample collection may occur immediately following the HIV screening or on a subsequent visit. Confirmatory testing usually takes 10-15 days; participants are usually discharged from the study hospital during this period and contacted later with the results.

Intervention arm. The VL test (below) will be used as the confirmatory test for HIV status.

CD4 T-cell Count

Control arm. Upon receipt of the HIV confirmatory results from the city CDC, participants will be asked to return to the study hospital for a blood draw for CD4 testing, often together with an initial epidemiological investigation. Blood specimens are sent to the city CDC for CD4 testing using plasma samples, which usually takes 10-15 days. Participants will be contacted and asked to return to the study hospital to receive the CD4 testing results and, if eligible, ART counseling.

Intervention arm. Blood samples for CD4 testing (and viral load) are collected at the study hospital immediately following receipt of positive HIV screening results. Numeration of CD4+ T-lymphocytes will be performed in the study hospital lab using a PIMA POC CD4 analyzer (Alere Healthcare, USA) using venous whole blood samples. POC CD4 testing results are available in less than 30 minutes.

Plasma HIV RNA VL Testing

Control arm. VL testing is performed only after ART initiation, about a year later. Blood samples for VL testing are collected at the study hospital.

Intervention arm. Blood samples for VL testing are collected at the study hospital (at the same time the CD4 sample is collected) immediately following receipt of positive HIV screening results and at the same time as the blood draw for CD4 testing (see above).

Both arms. VL testing is performed at the province CDC using plasma samples, which takes 10-15 days. Participants will be contacted and asked to return to the study hospital to receive the VL testing results and, if eligible, ART counseling.

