11.3 Safety Assessments

The intervention in this trial, comparing HIV testing strategies, poses no specific safety risk to the participants. HIV testing will involve several blood draws, up to 4 in SOC, and 1-3 in One4all arms. There will be no increase in the volume of blood drawn or the typical risk associated with blood draws. Standard of care will be compared to a new strategy (One4all) with a goal to improve HIV initiation of treatment in HIV screened positive cases. Risk of loss of confidentiality is a safety concern and will be managed throughout the study utilizing standard protections within the China health care system, and de-identified data will be used whenever possible. The study team extracting data from either the local hospital records or the CRIM system will assign a participant ID number to protect confidentiality of information. Any infringement or loss of confidentiality will be reported to the Chinese Ethics Committee for review and action if required. Throughout the course of the study, any deaths and hospitalizations will be captured through review of the hospital based care information systems and the CRIMS system. All of these events will be made available for ongoing monitoring by the Data and Safety Monitoring Board (DSMB). It is expected that there will be an initial review and approval of the protocol prior to study implementation. The DSMB will review for data and safety at the study halfway mark, e.g., 3-6 months from study start and a second review will be conducted as needed.

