12.3 Intervention Condition

Figure 8. New streamlined process for HIV testing and linkage to HIV care. Critical path to treatment highlighted by blue arrows.

[figure not shown]

New One4all Testing Algorithm (Figures 8-9).

Participants with HIV-positive screening results on EIA will immediately have their blood drawn for CD4 and VL tests. Two venous blood samples (4mL, and 10mL) will be collected—one for immediate numeration of CD4+ T-lymphocytes in the same hospital lab using a PIMA POC CD4 analyzer (Alere Healthcare, USA) and the other for later VL testing at the province CDC, which takes 10-15 days. Participants will be notified in-person of their CD4 results on the same day and provided post-CD4 test counseling (**Appendix C**). Counseling in the One4all intervention has been modified from the national SOC guidelines due to the different order of tests and the shortened time period between screening and CD4 testing. The participant will be provided with a tentative assessment of ART eligibility based on CD4 results and other factors. Those who are eligible for ART (**Appendix A**) are encouraged to seek HIV care at the study hospitals via China's National Free ART program. If indicated, the participant may begin preparation for ART initiation by completing a physical exam, other laboratory tests (liver, kidney, urinalysis), and medical insurance paperwork. ART initiation will not occur until the VL test is returned, which confirms HIV infection.

The VL serves as the confirmatory test for the One4all group and success for this group will be obtaining the results of the three EIAs, the POC CD4, the viral load, and the post-VL test counseling. Once the VL test results are available, the hospital will contact the participant by phone and ask him/her to return to the hospital for their results and post-VL test counseling (designated as the study endpoint post-test counseling). ART eligibility will be re-assessed based on the VL results. No confirmatory testing via WB will be conducted unless HIV status is not resolvable, a situation which is expected to be a rare occurrence. (44-47)

Figure 9. Detailed Study 1 Intervention procedures for HIV testing and linkage to HIV care in China. Patient pathway and timeframe is highlighted in blue.

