16.0 DATA MANAGEMENT AND PROCEDURES

16.1 Design and Development

A centralized Data and Statistics Team (DST) will be formed, composed of Drs. [name], [name], and [name], and [name] of NCAIDS and epidemiologists from the county CDCs related to each of the 12 participating study hospitals. The DST will be responsible for the validation of the web-based study database, and CRIMS, ensuring data integrity and security, and training the participating hospital and CDC staff on applicable data management procedures.

Data from this study are generated from one new study database system and one existing database. Using the case report forms (CRFs), we will collect baseline assessment information, including participant demographic information, laboratory screening results and dates, and tracking of test result notification dates and post-test counseling dates. The CRF data will then be stored in a newly designed web-based database for the study, which will serve as a centralized location for electronic storage of all study-related data. Study-related data from each hospital system will be retrieved weekly and uploaded to the web-based study database.

The existing database, CRIMS,(43) is a nationwide ongoing epidemiological database for confirmed HIV cases. CRIMS contains a unique code number for each county hospital nationwide, including all participating study hospitals. CRIMS stores information on HIV confirmatory testing, initial investigations of newly-diagnosed HIV cases, follow-up visits for each individual HIV/AIDS case, CD4 test, ART regimen, VL test, etc. Therefore, CRIMS can generate the following measures that can be used to construct study outcomes: the number of confirmed HIV cases; the number of participants who have received a CD4 test, their CD4 result, and the CD4 test date; the number of participants who have received VL test and the VL test date; and the number of participants who have initiated ART, the start date, and the ART regimen used. The CRIMS system will be used to supplement the web-based study database with any additional patient information that needs to be captured for study purposes.

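### Deaths may be captured unequally between arms, probably to the disadvantage of One4all, because one of the two named sources (CRIMS) covers only confirmed cases and the intervention changes confirmation

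*Protocol*

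**What the plan says.** Section 13.8 plans the protocol's only between-arm safety comparison: "Rates of hospitalizations and rates of mortality will be compared between the intervention arms as an assessment of safety". Section 11.3 says that "any deaths and hospitalizations will be captured through review of the hospital based care information systems and the CRIMS system"; the synopsis and section 15.12.3 repeat this.

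The two sources differ in coverage. Section 16.1 says that CRIMS "is a nationwide ongoing epidemiological database for confirmed HIV cases", and section 11.2.2 says when a record starts: "Participants who are confirmed HIV-positive (through WB or VL testing) will then have records created in CRIMS". Hospital systems cover anyone who attends, confirmed or not.

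The arms differ in the route to confirmation. Section 4.1 reports that in Guangxi "only 50.4% of those who screen HIV-positive at hospital settings receive confirmatory testing". For the Western blot sample under standard of care, section 11.2.4 says: "Blood sample collection may occur immediately following the HIV screening or on a subsequent visit". For One4all, section 12.3 says: "Participants with HIV-positive screening results on EIA will immediately have their blood drawn for CD4 and VL tests", and the viral load is the confirmatory test.

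Other provisions bear on capture. Section 11.2.2 also places dates of death and hospitalisations on study CRFs. Section 9.5 plans the same follow-up effort in both groups. Section 9.6 plans to re-contact all participants at 12 months. Section 6.2 specifies the 12-month CRF for viral load and treatment status, including medications. Table 1 in section 11.4 has no row for vital status or hospitalisation.

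**The concern.** Whether a death is seen should not depend on the assigned arm. Here it may. A standard-of-care participant who goes home before confirmation and dies elsewhere has no CRIMS record and may leave no trace in the study hospital. The same patient in One4all is more likely to have had a confirmatory sample taken at once, and so to have a CRIMS record on which the death is dated.

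The protocol's own background suggests that such deaths will occur. Section 4.1.1 gives a median of 5.2 months from confirmed diagnosis to death in Guangxi, and says that 79% of those who die of AIDS had never received ART. Section 11.2.4 notes that participants are usually discharged while the Western blot is pending.

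If capture is unequal in this way, equal true mortality would appear as an excess in One4all, and a real mortality benefit could be partly hidden.

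**Working it through.** The protocol gives no event rate, margin or capture share for the safety comparison, so it has no figure of its own to reproduce. The check is a simple capture model.

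**Inputs**
- c0, share of standard-of-care participants with a CRIMS record: 0.504, from section 4.1. This is a proxy: it is a historical share receiving confirmatory testing, not a share registered in CRIMS by 12 months.
- c1, the same share in One4all: not given, assumed 0.80 to 1.00. For orientation, the pilot in section 4.4 tested 88.1% of screen-positives and confirmed 282 of 338 (83%).
- h, the chance that a death in a participant without a CRIMS record is still found through hospital records, study CRFs or the 12-month contact: not given, varied from 0 to 1.
- Deaths in participants with a CRIMS record are assumed to be all found. True mortality is assumed equal between arms and between participants with and without a record, so it cancels from the ratio.

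**Formulas**
- Captured share in an arm = c + (1 − c) × h
- Apparent One4all/SOC ratio = [c1 + (1 − c1)h] / [c0 + (1 − c0)h]

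For h = 0.3, SOC captures 0.504 + 0.496 × 0.3 = 0.653. One4all captures 0.80 + 0.20 × 0.3 = 0.860 at the lower end and 1.00 at the upper end. The ratios are 0.860/0.653 = 1.32 and 1.00/0.653 = 1.53.

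| h | SOC captured | Ratio, c1 = 0.80 | Ratio, c1 = 0.881 | Ratio, c1 = 1.00 |
|---|---|---|---|---|
| 0 | 0.504 | 1.59 | 1.75 | 1.98 |
| 0.3 | 0.653 | 1.32 | 1.40 | 1.53 |
| 0.6 | 0.802 | 1.15 | 1.19 | 1.25 |
| 0.9 | 0.950 | 1.03 | 1.04 | 1.05 |
| 1 | 1.000 | 1.00 | 1.00 | 1.00 |

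**In counts.** Assume 10% true mortality, 180 per arm (18 deaths each), c1 = 0.881 and h = 0.5. SOC records 18 × (0.504 + 0.496 × 0.5) = 18 × 0.752 = 13.5 deaths. One4all records 18 × (0.881 + 0.119 × 0.5) = 18 × 0.9405 = 16.9. The ratio is 1.25 with no true difference.

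**Do the other sources bring h close to 1?** Section 11.2.2 has providers complete the follow-up CRFs from hospital systems and CRIMS, so the CRFs may inherit the same gap. The 12-month contact covers everyone, but vital status is not named as an item, and section 15.3 recognises that re-contact may not succeed. Section 7.5 leaves the chasing of missed appointments to clinical staff under usual practice. None of this fixes h.

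**The case against.** The strongest reply is that the protocol has sources that do not depend on confirmation. Study CRFs are kept for every enrolled participant and carry dates of death and hospitalisations. Section 9.5 plans equal follow-up effort, by phone and occasionally at the home address, with all attempts documented. Section 9.6 re-contacts everyone at 12 months. If these work well, h is high and the distortion is small: about 3-5% at h = 0.9. This stands, and it limits the point to a risk of unknown size.

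A reader might infer that unconfirmed standard-of-care patients can be seen only through the study hospital, so that the comparison is certainly biased. The CRF and re-contact provisions do not support that.

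A reader might also extend the point equally to hospitalisations. The documents do not support that either. General hospitalisations come from hospital systems and CRFs in both arms, and the CRIMS content listed in section 11.2.2 mentions only drug-related ones.

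The inputs are loose. The 50.4% is historical. Late Western blots still create CRIMS records. A One4all share of 100% is an outer bound, because enrolment rests on the initial EIA alone and false positives are never confirmed in either arm. These points weaken the upper end of the range but not the mechanism.

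Finally, mortality is not a primary, secondary or tertiary endpoint, so no planned efficacy claim depends on it. The protocol makes events available to the DSMB but describes no between-arm test there. It would go too far to say that the DSMB will act on a biased test. Its first review, at 3-6 months from study start, does however precede any 12-month contact.

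**Conclusion.** The point holds as a risk of differential ascertainment, chiefly of deaths outside the study hospital, and likely against One4all. The protocol itself fixes the three elements: a between-arm mortality comparison, a named source limited to confirmed cases, and an intervention that acts on confirmation. It does not mention the unequal coverage, and its mitigating sources are not specified so as to close the gap.

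The size cannot be determined from the document. With 50.4% against 80-100% confirmed, the spurious ratio is 1.00 if all deaths outside CRIMS are found, about 1.3-1.5 if 30% are found, and at most about 1.6-2.0 if none are. The direction rests on One4all confirming a larger share than standard of care, which the design intends but which is not yet known. Hospitalisations are much less affected, and the primary endpoint is not affected. The change is worth making but does not put the trial's main conclusion at stake.

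**What to change.** 1. In sections 6.2 and 9.6 and in Table 1, add two items to the 12-month CRF for every EIA-positive participant, confirmed or not: vital status (alive, dead with date, or unknown) and any hospitalisation since enrolment.
2. In section 13.8, base the between-arm mortality comparison on this source with all EIA-positive participants in the denominator, and show the unknown category by arm. That display matters because participants already in care may be easier to reach, so the 12-month contact may itself differ by arm.
3. Keep CRIMS deaths as a supplementary source, since discarding dated deaths would lose information. Add a sensitivity analysis limited to sources that do not depend on confirmation.
4. State in DSMB reports that capture may differ between arms, particularly before 12-month data exist.

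The cost is two CRF fields, a few sentences in the protocol and one additional sensitivity analysis. The contact itself is already planned for all participants.

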14.0 CONCOMITANT THERAPY

14.1 General Considerations for Participants Receiving ART

HIV-positive participants can have comorbidities with HIV-related diseases, including malignancies, hepatitis B and C, and non-AIDS related diseases, including diabetes mellitus, heart disease, and hypertension. Clinicians should be careful to monitor for drug-drug interactions and to adjust ART and opportunistic infection medications if needed. Women taking ART drugs that have significant pharmacokinetic interactions with oral contraceptives should use an additional or alternative contraceptive method.

For IDUs receiving methadone maintenance treatment, concurring ART may diminish the effectiveness of either or both therapies by causing opioid withdrawal or overdose, increased methadone toxicity, and/or decreased ART efficacy. Providers should prescribe and monitor appropriate dosages of methadone.

Deferral of ART may be considered when presentations of other medical conditions could complicate the treatment of HIV infection. An example is a previously scheduled surgery.

14.2 Medications Prohibited Before/During the Trial

Clinical data regarding on drug-drug interactions between ART and traditional Chinese medicines is insufficient. Participants are requested to avoid traditional medicines while receiving ART.

14.3 Medications Allowed During the Trial

14.3.1 Ancillary Medications

Any medication without known drug-drug interactions with ART may be used to treat concurrent conditions. Providers must review the safety, efficacy, and pharmacokinetic data provided by the manufacturing pharmaceutical company prior to prescription.

14.3.2 Rescue Medications

If participants present with any life-threatening conditions such as development of an allergic reaction or aggravation of concurrent disease, providers may decide to stop ART. Any appropriate rescue medications may be used.

15.0 REGULATORY COMPLIANCE AND SAFETY

15.1 Statement of Compliance

This trial will be conducted in compliance with the appropriate protocol, current Good Clinical Practice (GCP), the principles of the Declaration of Helsinki, and all other applicable regulatory requirements. Participating sites must obtain written approval of the study protocol, supporting documents, and any advertising for participant recruitment from the Chinese Ethics Committee in order to participate in the study. Prior to study initiation, the protocol will be reviewed by NIDA's Protocol Review Board/DSMB, and approved by the UCLA IRB and China CDC IRB. Any amendments to the protocol or study materials must be approved before they are implemented. Annual progress reports will be submitted to the IRBs, according to its usual procedures.

In the event of conflicting Chinese and US regulatory requirements, Chinese law will take precedence.

